**Control group.**

- 1) Unsatisfactory sample nucleic acid extraction
- 2) No spontaneous pregnancy at the time of follow-up

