## 1. Program Summary

Research Title	Establishment of a Rapid Detection Method for Microorganisms in the Lower Genital Tract Using MALDI-TOF MS and Its Clinical Application in Infertility
Purpose of the study	
1) Development and robustness evaluation of a rapid detection method based on Matrix-Assisted Laser Desorption/Ionization Time of Flight Mass Spectrometry (MALDI-TOF MS) for the simultaneous detection of multiple pathogens and CST in the lower genital tract
 
2) Assessment of the correlation between lower genital tract pathogenic infections, CST and infertility using the newly developed assay

Research Hypothesis	Possible correlation between CST, pathogens, and infertility in the lower genital tract
Study Design	Part I: Diagnostic tests; Part II: Case-control

Case group	Part I: MALDI-TOF MS test; Part II: Infertile individuals
Control group	Part I: Microbiological culture; Part II: Clinically proven to be spontaneous pregnancy
Sample size	Part I: 77 cases in each group; Part II: 114 cases in each group
Selection Criteria	
The first part of all test samples are acquired standards with no inclusion criteria; the second part:
 
Inclusion Criteria:
 
Case group:
 
 
1) Female aged 18-40
 
2) Regular menstrual cycle
 
2) Conform to the clinical diagnosis of infertility
 
3) No sexual life 3 days before the examination
 
 
control group:
 
 
1) Female aged 18-40
 
2) Regular menstrual cycle
 
3) Patients who did pre-pregnancy consultation in our hospital, pregnant at the time of 3-month follow-up
 
4) No sexual life 3 days before the examination
 
 
-
 
Exclusion Criteria:
 
Case group:
 
 
1) Infertility due to malformation of reproductive tract
 
2) Infertility caused by endocrine factors such as polycystic ovary syndrome, premature ovarian failure and severe hyperthyroidism
 
3) Infertility due to male factors
 
4) Patients with malignant tumors
 
5) Patients with autoimmune diseases
 
6) Patients with severe heart, kidney and other basic diseases
 
7) Patients who consumed antibiotics 3 days before the examination
 

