## 2. Research Background

### 1. 1 Research significance

The cervical canal and vagina (collectively referred to as the lower genital tract) are important components of the female reproductive tract, and infections of the lower genital tract are also the most common gynecologic conditions. Infections such as *Neisseria gonorrhoeae* (NG), *Mycoplasma urealyticum* (UU) and *Chlamydia trachomatis* (CT) not only cause discomfort, but may also lead to infertility, ectopic pregnancy, miscarriage and premature birth. These infections not only cause uncomfortable symptoms, but also may lead to infertility, ectopic pregnancy, miscarriage, premature birth and other adverse pregnancy outcomes, which seriously affect women's physical and mental health and family harmony. The infection may lead to infertility, ectopic pregnancy, miscarriage, preterm delivery and other adverse pregnancy outcomes, which can seriously affect women's physical and mental health and family harmony. Disruption of the ecosystem of the lower genital tract can lead to overgrowth of pathogens, resulting in vaginal infections and sexually transmitted infections (STIs). The disruption of the lower reproductive tract ecosystem can lead to an overgrowth of pathogens that can cause vaginal infections and sexually transmitted infections (STIs). The community state type (CST) of cervical and vaginal colonizing bacteria is the most important component of the lower genital tract microecosystem and has an important impact on the health of the lower genital tract. It has an important impact on the health of the lower reproductive tract. Recent studies have shown that abnormal CST is strongly associated with infertility and poor pregnancy outcomes. . Therefore, rapid, accurate and cost-effective detection of common pathogens and CST in the reproductive tract is a technique that gynecologists are eager to achieve, not only to comprehensively analyze the etiology

of infertility and poor pregnancy outcomes in patients, but also to further investigate the correlation between dynamic changes in CST and various pathogenic infections and diseases in the lower reproductive tract.

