#### **control group:**

- 1) Female aged 18-40
- 2) Regular menstrual cycle
- 3) Patients who did pre-pregnancy consultation in our hospital, pregnant at the time of 3-month follow-up
- 4) No sexual life 3 days before the examination

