#### 6.1.2 Part 2: Comparison of independent sample rates between the two groups

Comparison of the independent sample rates of the two groups: the infection rate of at least one pathogen in the whole population is about 0.01%, and the infection rate of patients who visited our hospital for infertility is about 0.46%, and this data was brought into SPSS software: Confidence Intervals for the Difference Between Two Proportions,  $n=114$  cases, so 114 cases were included in the experimental group and the control group each

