#### 6.2 Grouping method

Case group were patients with clinical diagnosis of infertility: sexually active, uncontraceptive and infertile for 2 years

The control group was those with spontaneous pregnancy: those with spontaneous pregnancy at the follow-up visit 3 months after consultation

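### Controls must be pregnant at the 3-month follow-up, so women who conceived spontaneously but lost the pregnancy are exited; if exposure raises early loss, this pushes the infertility odds ratio upward

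*Combined protocol and SAP*

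**What the plan says.** The control rule appears in four places.

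- Section 5.1, control group (repeated in the section 1 summary), admits "Patients who did pre-pregnancy consultation in our hospital, pregnant at the time of 3-month follow-up".
- Section 5.3, control group, exits a woman with "No spontaneous pregnancy at the time of follow-up".
- Section 6.2 defines the controls as "those with spontaneous pregnancy at the follow-up visit 3 months after consultation".
- The control-group line of the section 1 summary is looser: "Clinically proven to be spontaneous pregnancy", with no time point.

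Cases, in section 6.2, are "sexually active, uncontraceptive and infertile for 2 years".

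Section 1.1 says that infections such as gonococcus, mycoplasma and chlamydia "may also lead to infertility, ectopic pregnancy, miscarriage and premature birth". Sections 1.1 and 1.2 also link abnormal community state type (CST) to poor or adverse pregnancy outcomes.

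Objective 2 (section 3) concerns the association of infection and CST with infertility. No section mentions a pregnancy lost between consultation and follow-up. The form items listed in 8.2.2 include numbers of pregnancies and births, but not a loss in that window.

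**The concern.** A woman who conceives in the first month and miscarries in the second has shown the ability to conceive, which is what an infertility comparison contrasts. Under the rule she leaves the control group. She cannot be a case either, because she does not have two years of infertility. The control group therefore becomes women who conceived and were pregnant on the day of the visit.

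If loss is unrelated to exposure, this costs some controls and nothing else. If exposed women lose pregnancies more often, which the plan's own background raises as a possibility, exit depends on the exposure under study. The odds ratio for infertility then carries part of any effect on early loss, and it would exceed 1 even if exposure had no effect on conception. The chi-square, stratified and logistic analyses in section 12 use only the women retained, so they cannot undo this unless losses are recorded.

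**Working it through.** **Plan's own figure.** There is none to reproduce. The documents give no miscarriage rate, no relative risk of loss by exposure and no target odds ratio.

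**Formula.** Among women who conceive spontaneously, let a be exposed and b unexposed. Let m1 and m0 be the shares of these two groups who have lost the pregnancy and are not pregnant at the visit.

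- Exposure odds, all conceptions: a/b
- Exposure odds, retained controls: a(1−m1) / [b(1−m0)]
- The control odds are in the denominator of the odds ratio, so it is multiplied by (1−m0)/(1−m1), whatever the exposure prevalence.

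**Inputs (assumed).** m0 from 5% to 20%; relative risk of loss (RR) from 1 to 3; m1 = RR × m0.

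| m0 | RR 1 | RR 1.5 | RR 2 | RR 3 |
|---|---|---|---|---|
| 5% | 1.00 | 0.95/0.925 = 1.03 | 0.95/0.90 = 1.06 | 0.95/0.85 = 1.12 |
| 10% | 1.00 | 0.90/0.85 = 1.06 | 0.90/0.80 = 1.13 | 0.90/0.70 = 1.29 |
| 15% | 1.00 | 0.85/0.775 = 1.10 | 0.85/0.70 = 1.21 | 0.85/0.55 = 1.55 |
| 20% | 1.00 | 0.80/0.70 = 1.14 | 0.80/0.60 = 1.33 | 0.80/0.40 = 2.00 |

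For RR 1.5 to 2 the range is 1.03 to 1.33. The RR 3 column shows the sensitivity to the assumption; its last cell requires 60% loss in exposed women.

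**Effect on control prevalence (illustration).** Take a true prevalence of 7.3%, the upper mycoplasma figure in section 1.2, with m0 = 15% and RR = 2. The true odds are 0.073/0.927 = 0.0788. Multiplying by 0.70/0.85 gives 0.0649, a prevalence of 6.1%.

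**Comparison with sampling error.** Take 114 per group with 50% exposure in both, close to the most precise case: 57 women in each of four cells.

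- SE(log OR) = √(4/57) = 0.265
- 95% limits: multiply or divide by exp(1.96 × 0.265) = 1.68
- Factor 1.13 (unrounded 1.125): log = 0.118, or 0.44 SE
- Factor 1.33: log = 0.288, or 1.09 SE, still inside the 1.68 limits

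**At the planned infection rates.** Section 6.1.2 prints 0.01% for the whole population. That gives 114 × 0.0001 = 0.011 expected positive controls, or 1.14 if 0.01 is meant as a proportion. The shift in the pathogen comparison would be invisible on either reading. The plan gives no prevalence for abnormal CST, so this does not settle the CST comparison.

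**After the change.** If every confirmed spontaneous conception in the window counts, the factor from this source is 1.00. The 114 per group is unaffected.

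**The case against.** A reader might infer that the plan itself says the infections cause miscarriage, so that the rule necessarily lowers control exposure and inflates the odds ratio. The documents do not support that. Section 1.1 says only that they may lead to it. The examples of adverse outcomes given for chlamydia in section 1.2 do not include miscarriage, and CST is linked to poor outcomes generally, not to early loss. None of these links is quantified. The bias is conditional, and every loss risk above is an assumption.

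Other points on the plan's side:

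- *Losses are never mentioned, and one summary line has no time point.* True, but the criteria in the same summary, and sections 5.1, 5.3 and 6.2, supply the time point. As written this is a rule and not merely a gap.
- *Ongoing pregnancies may be intended.* Section 1.2 describes the comparison group as healthy women, and section 1.1 is also interested in poor pregnancy outcomes. This makes the primary control definition debatable. It does not argue against recording losses and reporting both comparisons.
- *The effect is probably towards the low end.* Late conceptions have little time at risk before the visit, and a woman who loses a pregnancy and conceives again stays eligible. An ectopic pregnancy present at the visit is not excluded by the text, which could act in the opposite direction. All of this stands.
- *It would not change the conclusion.* If the rates in 6.1.2 are proportions (0.46 against 0.01), the crude odds ratio is (0.46/0.54)/(0.01/0.99) ≈ 84, and a factor of 1.03 to 1.33 is immaterial. This stands for the pathogen comparison on that reading, but not necessarily for CST.
- *The same rule exits every woman who has simply not conceived in 3 months.* That selection towards rapid conceivers is probably larger. It is a separate matter and does not answer this one.

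**Conclusion.** The point holds in conditional form. The control rule, as written, exits women who conceived spontaneously and lost the pregnancy before the visit, and it does not match an objective about infertility. The resulting factor on the odds ratio is 1.00 if loss risks are equal, and about 1.03 to 1.33 for an assumed relative risk of 1.5 to 2 with m0 of 5% to 20%. It is away from the null only if exposure raises early loss, which the documents suggest as possible but do not quantify. The shift is small beside sampling error at 114 per group. It is worth correcting because the correction is cheap and because losses that are not recorded cannot be examined later, not because it is likely to overturn a result.

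**What to change.** In the section 1 summary and in sections 5.1, 5.3 and 6.2, define a control as a woman with a confirmed spontaneous conception at any time between the consultation and the 3-month follow-up, whether or not it is ongoing. Exit only women with no such conception. At follow-up, record pregnancy status and any loss since the consultation. Report the comparison restricted to ongoing pregnancies as a sensitivity analysis. If the sponsor prefers ongoing pregnancies as the primary control group, say so and give the reason, and report the comparison with losses included.

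Cost: wording in four places, one question at a follow-up that already takes place, and one additional analysis. Losses will be partly self-reported and very early ones will be missed, so some of the selection remains. The change does not address the separate selection of women who conceive within 3 months.

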## **6. estimation of sample size and grouping method**

### 6.1 Estimation of sample size

#### 6.1.1 Part I: Comparison of sensitivity of dose information between the two groups

Single and mixed standard bacterial solutions and blank controls were 11 in total, so the chance of the appearance of four microorganisms in various standard strain solutions was 0.18, and different studies showed that the culture sensitivity of gonococci, lactobacilli, mycoplasma, and chlamydia was 40-60% and specificity 95-98%; time-of-flight mass spectrometry detection was >99% in different studies, and the parameters were brought into

PASS according to  $\alpha=0.1$  Software calculation path: Tests for Two Independent Sensitivities,  $N=44-72$ , taking the least integer multiple of 11 for  $>72$ , i.e., 77 cases in each group

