	
8) Have the habit of smoking and drinking
 
Control group:
 
 
1) Pregnancy by various assisted reproductive means
 
2) Patients with malignant tumors
 
3) Patients with autoimmune diseases
 
4) Patients with severe heart, kidney and other basic diseases
 
5) Patients who consumed antibiotics 3 days before the examination
 
6) Have the habit of smoking and drinking
 

Exclusion Criteria
	
All samples tested in Part I were acquired standards with no inclusion criteria; Part II:
 
Case group:
 
 
1) Infertility due to malformation of reproductive tract
 
2) Infertility caused by endocrine factors such as polycystic ovary syndrome, premature ovarian failure and severe hyperthyroidism
 
3) Infertility due to male factors
 
4) Patients with malignant tumors
 
5) Patients with autoimmune diseases
 
6) Patients with severe heart, kidney and other basic diseases
 
7) Patients who consumed antibiotics 3 days before the examination
 
8) Have the habit of smoking and drinking
 
 
Control group:
 
 
1) Pregnancy by various assisted reproductive means
 
2) Patients with malignant tumors
 
3) Patients with autoimmune diseases
 
4) Patients with severe heart, kidney and other basic diseases
 
5) Patients who consumed antibiotics 3 days before the examination
 
6) Have the habit of smoking and drinking
 

Ending evaluation
	
Main indicators: microbiological test results, are recorded as negative, positive

indicators	
Safety evaluation indicators	Pain indicators: pain score; bleeding indicators: bleeding volume assessment (blood staining area method), blood routine; cervical and vaginal infection: white belt routine

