The vast majority of patients with lower genital tract pathogens are only transiently infected and can be cleared by their own or pharmacological treatment, while only a minority of patients have serious adverse outcomes, suggesting that other factors influence the pathogenic evolution of these pathogens. Previous studies have shown that the type and abundance of long-term parasitic flora in the human cavity are closely related to important aspects of disease development such as immune regulation, inflammatory response, cytogenetic mutation, angiogenesis, and tissue remodeling. . Therefore, in recent years, microecology has received a lot of attention from many fields such as immunity and metabolism. Since the discovery of *Lactobacillus vaginalis* by Albert Doderlein in 1982, a number of studies have been conducted to demonstrate that a decrease in the absence of *Lactobacillus vaginalis* is a major cause of inflammatory vaginal diseases such as mycobacteria and bacterial vaginitis. However, because early studies on genital tract pathogens were mainly performed by microbiological microscopy, staining, and culture, it was not possible to subtype *Lactobacillus*, and the correlation between lower genital tract CST and obstetrical and gynecological diseases has only recently been emphasized. Recently, many scholars have studied the relationship between vaginal CST and obstetric and gynecological diseases, and such studies have suggested that abnormal CST in the lower genital tract can lead to pelvic inflammatory disease infertility and adverse pregnancy outcomes. However, does abnormal CST promote gonorrhea? However, it is unclear whether CST abnormalities promote infection and persistence of infertility-causing pathogens such as *Neisseria gonorrhoeae*, *Mycoplasma*

urealyticum and Chlamydia trachomatis.

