Currently, most clinical tests for *Neisseria gonorrhoeae*, mycoplasma and chlamydia are performed using microbial cultures, and vaginal CST analysis is performed using 16SrRNA or macrogenomic sequencing. . Therefore, performing multiple analyses on a patient at the same time is not only expensive, but also requires multiple sampling, which affects the accuracy of the results and makes it difficult to be widely implemented in the clinic. To the best of our knowledge, there is no accurate and cost-effective method for simultaneous detection of common pathogenic microorganisms in the lower genital tract. Therefore, this study proposes to establish a combined detection system for common pathogens and CST in the lower genital tract based on the MALDI-TOF MS testing platform, which will enable clinicians to accurately detect pathogens and common microorganisms in the lower genital tract with a single sample at a reasonable testing cost, and provide more accurate information and evidence for patient disease status assessment and treatment guidance. In addition, the project team will evaluate and compare the lower genital tract microecology of infertile and healthy control women using the constructed assay, and initially explore the correlation between lower genital tract microecology and infertility, and the correlation between various pathogenic infections and lower genital tract CST.

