### **3. Purpose of the study**

1) Development and robustness of a rapid detection method for microorganisms in the lower genital tract based on time-of-flight mass spectrometry (MALDI-TOF MS) for simultaneous detection of multiple pathogens and CST

2) Assessment of the association between lower genital tract pathogenic infections, CST and infertility using a newly developed assay

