### 8. Research steps

#### **8.1 Part I. Development of a rapid detection method based on MALDI-TOF MS for simultaneous detection of multiple pathogens and CST in the lower genital tract and evaluation of diagnostic efficacy**

8.1.1 Find the relatively conserved regions of virulence factor sequences of each pathogen according to the database, intercept the specific sequences from the conserved regions of each pathogen to design multiplex PCR amplification primers and single base extension (SBE) primers for each strain to construct MALDI-TOF MS assays.

8.1.2 Purchase standard pathogen strains, culture standard concentrations (i.e., high concentrations) of standard pathogens using the culture method to identify standard pathogens and their activities

8.1.3 Formulation of single, mixed and negative control standards with standard pathogens.

8.1.4 Gold standard: The actual pathogen type added to the standard is the gold standard.

8.1.5 Detection of standards at gradient dilution concentrations by incubation method and MALDI-TOF MS, respectively.

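### Part I claims to evaluate an assay for pathogens and CST, but no planned Part I result measures whether a CST is assigned correctly; Part II then analyses CST with that assay

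*Combined protocol and SAP*

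**What the plan says.** **The claim.** Section 3 describes a rapid method "for simultaneous detection of multiple pathogens and CST" and includes its robustness in the aim. The heading of section 8.1 covers "simultaneous detection of multiple pathogens and CST in the lower genital tract and evaluation of diagnostic efficacy". CST is therefore inside what Part I is said to evaluate.

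**The Part I procedure.**
- Primer design (8.1.1): "Find the relatively conserved regions of virulence factor sequences of each pathogen according to the database". No CST-defining marker is named.
- Test material (8.1.3): "Formulation of single, mixed and negative control standards with standard pathogens".
- Gold standard (8.1.4): the organism type put into each standard.
- Testing (8.1.5): graded dilutions, by culture and by MALDI-TOF MS.
- Recorded result: the Program Summary has "Main indicators: microbiological test results, are recorded as negative, positive". Section 10.2 is more specific and records the microbial type as well as positive or negative.
- Analysis (section 12): Se, Sp, PV+ and PV-.
- Sample size (6.1.1): built on the "culture sensitivity of gonococci, lactobacilli, mycoplasma, and chlamydia", giving 77 per group.

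**Use in Part II.** Women's samples are tested with the constructed assay (8.2.5). CST status is then related to infertility (8.2.6) and compared between infected and uninfected women (8.2.7).

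**The concern.** A CST describes a community, and the text gives no CST categories, no rule for assigning one and no measure of agreement. The protocol's background shows that CST is a different task from finding an organism. Section 1.2 says that "vaginal CST analysis is performed using 16SrRNA or macrogenomic sequencing". It also says of early work based on microscopy, staining and culture that "it was not possible to subtype" Lactobacillus, and it links the type and abundance of resident flora to disease.

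Two things are at stake. Good Part I figures for organism detection would appear under a heading that also names CST. And the Part II associations involving CST, which serve the second objective, would rest on a classification whose error rate nobody has estimated. A CST definition added later would not cure this by itself, because the Part I standards, recorded result and metrics would still not test the assignment.

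**Working it through.** **1. Reproduce the plan's 77.**

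Inputs from 6.1.1: 11 solution types; chance of an organism appearing 0.18 (2/11 = 0.182); culture sensitivity 0.40 to 0.60; MALDI-TOF MS above 0.99, taken as 0.99; alpha 0.1. Power and sidedness are not stated. Of the variants tried, the closest match is a two-sided pooled z-test with exact binomial power of 0.90, so those two settings are assumptions.

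- 0.99 against 0.40: 8 positives per group; 8 / 0.18 = 44.4.
- 0.99 against 0.60: 13 positives per group; 13 / 0.18 = 72.2.

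This gives the plan's 44-72, and the next multiple of 11 is 77. The figure is therefore the size for one binary sensitivity comparison. At 77 tests an organism is present in 77 × 2/11 = 14. No input describes a CST category, a proportion or an agreement target, so no corrected size for CST can be derived from the documents.

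**2. Set the claim beside the planned outputs.**

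| Element | What it can show | CST assignment? |
|---|---|---|
| Gold standard (8.1.4) | which organism type was added | no CST label for any standard |
| Recorded result (10.2) | type, positive or negative | no CST, dominance or proportion |
| Dilutions (8.1.5) | detection at lower concentrations | still read as detected or not |
| Se, Sp, PV+, PV- (section 12) | accuracy of detection | no CST agreement measure |
| 77 per group (6.1.1) | precision for detection | no CST input |

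**3. Can the target list be recovered from 6.1.1?** Only by inference, and the figures do not settle it.
- Four organisms as singles, all pairs and one blank make 4 + 6 + 1 = 11 solutions, but each organism would then appear in 4/11 = 0.36 of them, not 0.18.
- Nine single-strain solutions, one mixture of all strains and one blank also make 11, with each strain in 2/11 = 0.18.
- Four targets, each in one single and one mixed solution, use at most 4 + 2 = 6 solutions and leave at least five blanks.

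The 0.18 is thus compatible with more than four strains, possibly including several Lactobacillus species. The text does not say so, and the flow charts in section 9 are not shown.

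**4. Illustration of what unknown CST error could do in Part II.** Every input is assumed: a binary CST, abnormal in 30% of controls and 46% of cases, with a proportion e misassigned equally in both groups and both directions. Observed rate = p(1 − e) + (1 − p)e.

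| e | Controls | Cases | Odds ratio |
|---|---|---|---|
| 0 | 0.300 | 0.460 | (0.46/0.54)/(0.30/0.70) = 1.99 |
| 5% | 0.320 | 0.464 | (0.464/0.536)/(0.32/0.68) = 1.84 |
| 10% | 0.340 | 0.468 | (0.468/0.532)/(0.34/0.66) = 1.71 |
| 20% | 0.380 | 0.476 | (0.476/0.524)/(0.38/0.62) = 1.48 |

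**The case against.** The best defence is that Part I is more informative than the Program Summary's bare positive/negative suggests.

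- **Type is recorded.** Section 10.2 records microbial type, and 8.1.4 judges it against the type added. If several Lactobacillus species are separate targets and CST is assigned from which species are present, species-level sensitivity and specificity would test the components of that rule. This stands. A reader might infer that Part I is uninformative about CST under any definition; that is true only of a rule based on abundance or dominance, and the documents state no rule.
- **Lactobacilli as one target.** A reader might infer this from 6.1.1. The sentence there reports culture sensitivities from other studies and is not a list of assay targets; 8.1.1 speaks of primers for each strain.
- **Culture's limits.** A reader might infer that culture's inability to subtype Lactobacillus invalidates Part I. It does not: the remark concerns early studies, and culture is only the comparator.
- **Reporting.** Section 12 plans no CST accuracy claim, and section 1.2 describes the correlation work as initial exploration. It cannot be said that the sponsor will report organism accuracy as CST accuracy.

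What the defence does not reach is the stated aim. CST is named in the evaluation, yet no output assesses assignment, even for a presence-based rule, since accuracy for components is not accuracy for the combined class.

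**Conclusion.** The point holds as a gap between the stated aim and the design. Part I, as written, supports conclusions about detecting the organisms tested. It supports none about correct assignment of a CST, which 8.2.6 and 8.2.7 then analyse. The pathogen-detection comparison and its 77 per group are unaffected by this point.

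The size of the effect on Part II cannot be determined from the documents. The fall from an odds ratio of 2.0 to between 1.84 and 1.48 depends wholly on assumed prevalences, an assumed error rate that is equal in cases and controls, and a binary CST. It shows possible attenuation. A reader might take it as the expected bias, or as a sign that error of this kind would create an association; neither follows.

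The conclusion rests on the text of sections 6, 8, 10 and 12. A CST step in the flow charts, which are not shown, cannot be excluded.

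**What to change.** **Minimum, wording only.** Restrict the Part I accuracy conclusion to detection of the organisms actually tested, and list them. Label the CST analyses in 8.2.6 and 8.2.7 as exploratory and based on a classification not validated in Part I. The cost is a narrower stated conclusion.

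**Optional, if the CST claim is to be kept.** Fix the CST categories and the assignment rule in advance, add mixed standards with known Lactobacillus species and proportions, record the information that the rule needs, and report agreement with the known mixture. The logic of 8.1.4 allows this, since what was added is the reference.

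These standards should be added to the existing 77 tests unless the positives per organism are preserved. Assuming equal replication, each solution accounts for 77 / 11 = 7 tests. Replacing one of the two solutions that contain an organism would cut its positives from 14 to 7, against the 8 to 13 needed in the reproduction above. Each extra solution at the same replication costs 7 further tests per method, plus the purchased strains. Even then, agreement would be shown only in prepared mixtures and not in clinical secretions, and the report should say so.

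### Part I is sized as 77 independent specimens in each of two independent groups, but the tests are paired and grouped on 11 standards, and the robustness objective has no analysis

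*Combined protocol and SAP*

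**What the plan says.** Section 6.1.1 describes the test material: "Single and mixed standard bacterial solutions and blank controls were 11 in total". It continues: "so the chance of the appearance of four microorganisms in various standard strain solutions was 0.18". It takes "culture sensitivity of gonococci, lactobacilli, mycoplasma, and chlamydia was 40-60% and specificity 95-98" per cent for culture and, for the new assay, "time-of-flight mass spectrometry detection was >99% in different studies". With alpha 0.1, the PASS procedure for two independent sensitivities gives N = 44 to 72. The plan then rounds by "taking the least integer multiple of 11" above 72 and arrives at "77 cases in each group".

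Sections 8.1.3 to 8.1.5 describe one set of single, mixed and negative-control standards, then: "Detection of standards at gradient dilution concentrations by incubation method and MALDI-TOF MS, respectively". The true content of each standard is the gold standard (8.1.4).

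The Program Summary gives the first aim as "Development and robustness evaluation of a rapid detection method", and section 3 repeats it in similar words. For Part I, section 12 lists only sensitivity, specificity and the two predictive values.

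**The concern.** The calculation assumes that every positive result comes from its own specimen and that the two methods are applied to separate groups. Part I has a small set of standards, each tested several times and by both methods. If the comparison with culture is analysed as it was sized, its false-positive rate is not the nominal 0.10. A single pooled sensitivity would also hide how detection varies with concentration, which is the purpose of a dilution series. Separately, a stated aim, robustness, would end the study with no result, although tests already planned could supply one.

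**Working it through.** **Inputs from section 6.1.1.** 11 standards; prevalence 0.18; culture sensitivity 0.40 to 0.60; MALDI-TOF MS sensitivity taken as 0.99; alpha 0.1; N = 44 to 72, rounded to 77. Not stated: sidedness, power, within-solution correlation, and the numbers of preparations, dilution levels and repeats.

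**1. Reproducing 77.** I used a two-sided pooled Z test of two independent proportions, alpha 0.10, with power by exact binomial enumeration.
- 0.40 v 0.99: 8 positives per group give power 0.922 (7 give 0.889). 8 / 0.18 = 44.4.
- 0.60 v 0.99: 13 positives per group give power 0.904 (12 give 0.875). 13 / 0.18 = 72.2.

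Both ends of the range are recovered at an assumed power of 0.90. The next multiple of 11 is 77, so the arithmetic stands, and it contains no allowance for repeated or paired testing.

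**2. What 77 consists of.** 77 / 11 = 7 tests per solution per method. 2 / 11 = 0.18, so each organism is in 2 solutions. 2 × 7 = 14 positive tests per organism per method (77 × 0.18 = 13.9).

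**3. Layout A: the tests of a solution share a preparation.** I gave each method 2 solutions × 7 tests with beta-binomial counts, true sensitivity 0.60 for both methods, and applied the test from step 1 with 14 positives per group. The intraclass correlation (ICC) is assumed. Solution effects are drawn independently for the two methods; preparation error that moves both methods the same way would reduce the inflation.

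| ICC | Type I error (nominal 0.10) |
|---|---|
| 0 | 0.10 |
| 0.1 | 0.20 |
| 0.3 | 0.36 |
| 0.5 | 0.47 |

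**4. Layout B: the 7 tests are fixed dilution levels, with outcomes independent given the level.** Assume detection probabilities of 1, 0.98, 0.90, 0.70, 0.40, 0.15 and 0.05.
- Mean: 4.18 / 7 = 0.597.
- Variance of the positive count over two solutions: 2 × Σp(1 − p) = 2 × 0.7346 = 1.47.
- Binomial variance at the same mean: 14 × 0.597 × 0.403 = 3.37.
- Type I error of the same test with this profile in both methods: about 0.01.

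The test is now conservative. The pooled figure also depends on the levels chosen: without the two lowest it would be 3.98 / 5 = 0.80 rather than 0.60, with no change in the assay.

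**5. Pairing.** Take 14 pairs, exact McNemar at two-sided 0.10, with pairs independent of one another and the two methods' outcomes independent within a pair. Power is 0.68 at culture sensitivity 0.60 and 0.97 at 0.40. The independent-groups calculation with 14 positives gives 0.93 and 0.997.

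**6. Robustness.** The aim appears in the Program Summary and section 3. None of the four measures in section 12 describes agreement among repeated tests of the same material.

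**The case against.** The strongest reply is that the layout is inferred. The text nowhere says that each solution is tested 7 times, or from one preparation. The 11 solutions are not listed, and the section 9 flow chart, which might show the layout, is not in the text available. This stands as a limit on the size of the problem. It does not remove it: the 11 solutions are the only reason given for a multiple of 11, and 0.18 matches 2 of 11. A set of four singles, six pairs and one blank would also make 11, but would put each organism in 4 solutions (4 / 11 = 0.36), which does not match.

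A reader might infer that the 7 tests of a solution succeed or fail together, so that 77 can be deflated by a design effect to a definite loss of power. The documents do not support this. They give no ICC, and section 8.1.5 specifies a dilution gradient, under which outcomes within a solution are meant to differ and the bias can run the other way (step 4). If every test came from a separately prepared aliquot, and inference were limited to these strains and concentrations, the correlation could be near zero. The paired design would still not match the independent-groups calculation.

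A reader might also infer that the planned confidence intervals for sensitivity are too narrow. Section 12 plans none. It names no test against culture for Part I either; the comparison is implied by the title and method of section 6.1.1.

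**Conclusion.** The independent-specimen, independent-group basis of 77 does not match the design in section 8.1. The figure itself is calculated correctly for the model chosen, if power was 0.90. The consequence is an error rate that the plan does not control: about 0.20 to 0.47 against a nominal 0.10 if tests share a preparation with an ICC of 0.1 to 0.5, or about 0.01 under the assumed dilution profile. Which applies cannot be settled until the layout is stated. These figures rest on the assumed ICCs and detection probabilities, and on the inferred 7 tests per solution and 2 positive solutions per organism. Two parts do not depend on those assumptions: both methods test the same standards, so the comparison is paired; and the robustness aim has no analysis.

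**What to change.** In section 6.1.1, restate 77 as tests on 11 solutions per method (per organism, about 14 positive tests from 2 solutions). Give the split into independent preparations, dilution levels and repeats, and state the power and sidedness used. Have each preparation coded and split between the two methods.

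In section 12:
- Compare the methods in pairs with the preparation as the unit, for example by exact McNemar where each pair is a separate preparation, or by a bootstrap over preparations pooled across organisms. A mixed logistic model is a poor choice here: with two positive solutions per organism and sensitivity near 0.99, it could not estimate a solution variance.
- Report sensitivity by concentration, and limit inference to the strains and concentrations tested.
- Report agreement among repeats at the same concentration as the repeatability result for the robustness aim. Agreement across different dilutions would not serve, so the 7 tests per solution must include some repeats at one level.

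The cost is some extra pipetting and new wording in two sections. No more tests are needed. The downside is possibly wider intervals or lower stated power (step 5). The layout should be fixed before testing starts, because independent preparation cannot be added afterwards.
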